### **5.3. Procedures for Maintaining and Breaking the Masking**

Under normal circumstances, the mask should not be broken until all subjects have completed the study and the database is finalized. Otherwise, the mask should be broken only if specific emergency treatment/course of action would be dictated by knowing the treatment status of the

# **Clinical Study Protocol**

## **Johnson & Johnson Vision Care, Inc.**

subject. In such cases, the Investigator may, in an emergency, contact the medical monitor. In the event the mask is broken, the Sponsor must be informed as soon as possible. The date, time, and reason for the unmasking must be documented in the subject record. The Investigator is also advised not to reveal the study treatment assignment to the clinical site or Sponsor personnel.

When dispensing test articles, the following steps should be followed to maintain randomization codes:

1. Investigator or designee (documented on the Delegation Log) will consult the randomization scheme to obtain the test article assignment for that subject prior to dispensing
2. Investigator or designee will record the subject's number on the appropriate line of the randomization scheme
3. Investigator or designee will pull the appropriate test articles from the study supply. All test articles that are opened, whether dispensed (placed/fit on eye or dispensed outside the clinical site) or not, must be recorded on the Test Article Accountability Log in the "Dispensed" section.

## **6. STUDY INTERVENTION**

### **6.1. Identity of Test Articles**

Table 1: Lubricating eye drops

|                           | Test  | Control                       |
|---------------------------|---|-------------------------------|
| Solution Name/Description | Investigational lipid eye drops
[REDACTED]   | Blink® Tears                  |
| Manufacturer              | Johnson & Johnson Vision, Inc   | Johnson & Johnson Vision, Inc |
| Ingredients               | Castor Oil, Polyoxy 40
Hydrogenated Castor Oil,
Sodium Chlorite, Boric Acid,
Sodium Borate Decahydrate,
Sodium Chloride, Potassium
Chloride, Calcium Chloride
Dihydrate, Magnesium Chloride
Hexahydrate, Polyethylene
Glycol 400, Sodium
Hyaluronate, Purified Water | See package insert            |
| Packaging Form            | Over-Labeled  | Over-Labeled                  |

# **Clinical Study Protocol**

## **Johnson & Johnson Vision Care, Inc.**

### **6.2. Ancillary Supplies/Products**

ScleralFil (Bausch + Lomb) or LacriPure (Menicon) or other country-specific alternative approved by the sponsor may be used to rinse the eye following instillation of Sodium fluorescein dye.

Table 1: Ancillary Supplies

| Solution Name/Description  | Solution                                       |   |   |
|--|--|---|---|
|  | ScleralFil (or other sponsor-approved product) | Lacripure (or other sponsor-approved product) | Fluorescein (or other sponsor-approved product) |
| Manufacturer   | Bausch + Lomb                                  | Menicon                                       | Akorn, Inc                                      |
| Preservative   | None   | None  | None  |
| Other distinguishing items (dye, packaging, approval status, etc.) | NA   | NA  | D&C Yellow No. 8, 0.6 mg                        |

[figure not shown]
Sodium fluorescein dye will be used for biomicroscopy, as needed. Sterile, preservative-free, saline may be used in this clinical study to rinse each eye.

### **6.3. Administration of Test Articles**

Test articles will be administered to subjects meeting all eligibility requirements set forth in this clinical protocol. Lost or damaged test articles will not be replaced at the discretion of the Investigator and/or the Sponsor.

### **6.4. Packaging and Labeling**

The test articles will be packaged in bottles as the primary packaging. The test article will be over-labeled to mask the subject to the identity. The test articles will be in investigational cartons sealed with a tamper evident seal, commercial cartons, or in plastic bags as the secondary packaging form. The labels for the primary and secondary packages will contain the following message, in accordance with JJV over-labeling procedures for masked studies involving marketed products: "For Use in Clinical Study CR-6371, Eye Drops. CAUTION – For Investigational Use Only." The labels will also contain the product code, lot number, expiration date and the clinical study number.

# **Clinical Study Protocol**

## **Johnson & Johnson Vision Care, Inc.**

### **6.5. Storage Conditions**

Test articles will be maintained at ambient temperatures at the clinical site. Test articles must be kept under secure conditions.

### **6.6. Collection and Storage of Samples**

When possible, any test article associated with an Adverse Event and/or a Product Quality Complaint must be retained pending directions from the sponsor for potential return to JJVC.

### **6.7. Accountability of Test Articles**

JJVC will provide the Investigator with sufficient quantities of study articles and supplies to complete the investigation. The Investigator is asked to retain all lens shipment documentation for the test article accountability records.

Test articles must be kept in a locked storage cabinet, accessible only to those assigned by the Investigator for dispensing. The Investigator may delegate this activity to authorized study site personnel listed on the Site Delegation Log. All test articles must be accounted. This includes:

1. What was dispensed to the subject for in-office use.
2. What was returned to the Investigator unused, including expired or malfunctioning product.
3. The number and reason for unplanned replacements.

The Investigator will collect all unused test articles from the subjects at the end of the subject's participation. Subject returned unused test articles must be separated from the clinical study inventory of un-dispensed test articles and must be labeled with the subject number and date of return. Following final reconciliation of test articles by the monitor, the Investigator or monitor will return all unused test articles to JJVC.

If there is a discrepancy between the shipment documents and the contents, contact the study monitor immediately.

**Clinical Study Protocol**  
**Johnson & Johnson Vision Care, Inc.**

**7. STUDY EVALUATIONS**

**7.1. Time and Event Schedule**

Table 2: Time and Events

| Visit Information                      | Visit 1
Baseline,
dispense
drop |
|--|--|
| Time Point                             | Day 0                                    |
| Estimated Visit Duration               | 3 hours                                  |
| Study Informed Consent                 | X  |
| Inclusion/Exclusion Screening Criteria | X  |
| Demographics                           | X  |
| Medical History & medication review    | X  |
| Entrance Snellen VA                    | X  |
| Biomicroscopy                          | X  |
| Eligibility                            | X  |
| Randomization                          | X  |
| Baseline logMAR                        | X  |
| Instillation of drop #1                | X  |
| Ocular symptoms                        | X  |
| 3-minute post drop #1 logMAR           | X  |
| 10-minute post drop #1 logMAR          | X  |
| 90-minute washout                      | X  |
| Instillation of drop #2                | X  |
| Ocular symptoms                        | X  |
| 3-minute post drop #2 logMAR           | X  |
| 10-minute post drop #2 logMAR          | X  |
| Exit Slit-lamp                         | X  |
| Exit Snellen VA                        | X  |
| Final Evaluation                       | X  |

# Clinical Study Protocol

## Johnson & Johnson Vision Care, Inc.

### 7.2. Detailed Study Procedures

#### VISIT 1

Subjects should attend the Visit 1 while wearing their habitual contact lenses.

| Visit 1: Screening |  |   |
|--------------------|--|---|
| Step               | Procedure  | Details   |
| 1.1                | Statement of Informed Consent                            | 
Each subject must read, understand, and sign the Statement of Informed Consent before being enrolled into the study. The Principal Investigator or his/her designee conducting the informed consent discussion must also sign the consent form.
 
NOTE: The subject must be provided a signed copy of this document.
                                  |
| 1.2                | Demographics   | Record the subject's date of birth, gender, race and ethnicity.   |
| 1.3                | Medical History and Concomitant Medications              | Questions regarding the subjects' medical history and concomitant medications.  |
| 1.4                | Habitual Lenses  | Questions regarding the subject's habitual lens type and parameters.  |
| 1.5                | Wear time and comfortable wear time with Habitual Lenses | Record the subject's wear time and comfortable wear time with their habitual contact lenses.  |
| 1.6                | Eligibility after Screening                              | 
All responses to Screening Inclusion Criteria questions must be answered "yes" and all responses to Exclusion Criteria must be answered "no" for the subject to be considered eligible.
 
If subject is deemed to be ineligible after screening, proceed to Final Evaluation and complete Subject Disposition. Refraction and Biomicroscopy forms are not required.
 |

| Visit 1: Baseline |                        |   |
|-------------------|------------------------|---|
| Step              | Procedure              | Details   |
| 1.7               | Entrance Visual Acuity | Record the distance Snellen visual acuity (OD, OS, and OU) to the nearest letter with their habitual contact lens correction in place. Subjects must read the smallest line until at least 50% of the letters are read incorrectly. |

**Clinical Study Protocol**  
**Johnson & Johnson Vision Care, Inc.**

| Visit 1: Baseline |  |   |
|-------------------|--|---|
| Step              | Procedure                                    | Details   |
| 1.8               | Baseline SROS                                | Subjects will respond to a verbal open-ended symptoms questionnaire.  |
| 1.9               | Remove habitual Contact lenses               | Remove habitual contact lenses and store in a case with non-preserved saline.   |
| 1.10              | Slit Lamp Biomicroscopy                      | 
FDA Slit Lamp Classification Scale will be used to grade the findings and determine eligibility.
 
If any of these slit lamp findings are grade 3 or higher, the subject may not continue at this time, but may return up to one additional time to determine eligibility. If discontinued a final examination must be completed.
 
If the clearance of the fluorescein needs to be expedited, preservative-free rewetting drops or saline may be instilled.
 |
| 1.11              | Eligibility after Baseline                   | 
All responses to Inclusion Criteria questions must be answered “yes” and all responses to Exclusion Criteria questions must be answered “no” for the subject to be considered eligible.
 
If subject is deemed to be ineligible after baseline, proceed to Final Evaluation and complete all forms.
   |
| 1.12              | Reinsert habitual lenses                     | Habitual lenses will be reinserted  |
| 1.13              | Settling time                                | Allow habitual lenses 5 minutes to settle.  |
| 1.14              | Baseline Distance ETDRS LogMAR Visual Acuity | Under high illumination and high chart luminance, record the distance (4 meter) ETDRS low contrast visual acuity OD (LC1) and OS (LC2).   |

| Visit 1: Treatment 1 |                   |   |
|----------------------|-------------------|---|
| Step                 | Procedure         | Details   |
| 1.15                 | Drop Selection    | Assign the study drop based on the randomization scheme.  |
| 1.16                 | Drop Instillation | The Investigator or technician will instill 1 drop in the right eye. Wait 1 minute and then instill 1 drop in the left eye. |

**Clinical Study Protocol**  
**Johnson & Johnson Vision Care, Inc.**

| Visit 1: Treatment 1 |   |  |
|----------------------|---|--|
| Step                 | Procedure   | Details  |
| 1.17                 | Ocular Symptoms   | Subjects will respond to a verbal open-ended symptoms questionnaire.   |
| 1.18                 | Drop Settling   | Allow the drop to settle for 3 minutes (from OD drop).   |
| 1.19                 | 3-minute Distance
ETDRS LogMAR
Visual Acuity (from OD drop time)  | Under high illumination and high chart luminance, record the distance (4 meter)
ETDRS low contrast visual acuity OD (LC3) and OS (LC4).           |
| 1.20                 | 10-minute Distance
ETDRS LogMAR
Visual Acuity (from OD drop time) | Under high illumination and high chart luminance, record the distance (4 meter)
ETDRS low contrast visual acuity OD (LC1) and OS (LC2).           |
| 1.21                 | Drop Wash out   | Allow a washout of at least 90 minutes before continuing to the second eye drop (subject continue to wear habitual contact lenses during this time). |

| Visit 1: Treatment 2 |   |  |
|----------------------|---|--|
| Step                 | Procedure   | Details  |
| 1.22                 | Drop Instillation   | The Investigator or technician will instill 1 drop in right eye, wait 1 minute and then instill 1 drop in the left eye.                    |
| 1.23                 | Ocular Symptoms   | Subjects will respond to a verbal open-ended symptoms questionnaire.   |
| 1.24                 | Drop Settling   | Allow the drop to settle for 3 minutes (from OD drop time).  |
| 1.25                 | 3-minute Distance
ETDRS LogMAR
Visual Acuity (from OD drop time)  | Under high illumination and high chart luminance, record the distance (4 meter)
ETDRS low contrast visual acuity OD (LC3) and OS (LC4). |
| 1.26                 | 10-minute Distance
ETDRS LogMAR
Visual Acuity (from OD drop time) | Under high illumination and high chart luminance, record the distance (4 meter)
ETDRS low contrast visual acuity OD (LC1) and OS (LC2). |
| 1.27                 | Remove habitual Contact lenses  | Remove habitual contact lenses and store in a case with non-preserved saline.  |

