#### **1.4. Summary of Known Risks and Benefits to Human Subjects**

The following risks/adverse events can be associated with using lubricating eye drops and contact lenses, in general:

- There may be less comfort than when the drop was first placed on the eye.
- The eyes may burn, sting and/or itch.
- There may be a feeling of something in the eye (foreign body, scratched area).
- There may be the potential for some temporary impairment due to peripheral infiltrates, peripheral corneal ulcers and corneal erosion.
- There may be the potential for other physiological observations, such as local or generalized edema, corneal neovascularization, corneal staining, injection, tarsal abnormalities, iritis and conjunctivitis, some of which are clinically acceptable in low amounts.
- There may be excessive watering, unusual eye secretions, or redness of the eye.

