# **Clinical Study Protocol**

## **Johnson & Johnson Vision Care, Inc.**

- Subject lost to follow-up
- Subject no longer meets eligibility criteria (e.g. the subject becomes pregnant)
- Subject develops significant or serious adverse events causing discontinuation of study drop
- Subjects who have experienced a Corneal Infiltrative Event (CIE)
- Investigator's clinical judgment regarding the subject safety reasons (that it is in the best interest of the subject to stop treatment)
- Subject not successfully dispensed due to lack of efficacy or safety.

For discontinued subjects, the Investigator will:

- Complete the current visit (scheduled or unscheduled)
- Complete the Final Evaluation, indicating the reason that the subject was discontinued from the study

An additional subject may be enrolled if a subject discontinues from the study prematurely.

In cases where a subject is lost to follow-up, every possible effort must be made to contact the subject and determine the reason for discontinuation/withdrawal. The measures taken to follow up must be documented including two written attempts and a certified letter (or equivalent) as the final attempt.

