### **13.3. Documentation and Follow-Up of Adverse Events**

The recording and documenting of adverse events (ocular and non-ocular) begin when the subjects are exposed to the test article, study treatment or study procedure. Adverse events reported before the use of test article, start of study treatment, or study procedures will be recorded as medical history. However, if the condition deteriorates at any time during the study it will be recorded and reported as an AE. Untoward medical events reported after the subject's exit from the study will be recorded as adverse events at the discretion of the Investigator.

Upon finding an adverse event, the Principal Investigator will document the condition in the subject record and in the eCRFs. He/she will complete the Adverse Event /eCRF.

Complete descriptions of all adverse events must be available in the subject record. All Adverse Events including local and systemic reactions not meeting the criteria for “serious adverse events” shall be captured on the appropriate case report form or electronic data system. All adverse events occurring while the subject is enrolled in the study must be documented appropriately regardless of relationship.

It is the Investigator's responsibility to maintain documentation of each reported adverse event. All adverse events will be followed in accordance with applicable licensing requirements. Such documentation will include the following:

- Adverse event (diagnosis not symptom).
- Drawings or photographs (where appropriate) that detail the finding (e.g., size, location, and depth, etc.).

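### Symptoms are asked once per drop, before the 3-minute reading, and not again before drop 2 or at exit, so late symptom-only reactions are not actively sought and drop 2 has no symptom baseline

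*Combined protocol and SAP*

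**What the plan says.** Section 7.2 asks about symptoms three times: at baseline before any drop (step 1.8), after drop 1 (step 1.17) and after drop 2 (step 1.23). Each time the instruction is the same: "Subjects will respond to a verbal open-ended symptoms questionnaire". The post-drop question follows instillation, where step 1.16 reads "Wait 1 minute and then instill 1 drop in the left eye", and precedes the settling step, "Allow the drop to settle for 3 minutes (from OD drop". The Time and Events table in 7.1 keeps this order, with a row "Ocular symptoms" after each instillation and before each 3-minute logMAR reading.

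After the 10-minute reading, step 1.21 says "Allow a washout of at least 90 minutes before continuing to the second eye drop", and step 1.22 instils drop 2. The Final Evaluation has the exit form (F.1), slit lamp (F.2) and Snellen acuity (F.3).

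Section 1.4 opens its list of risks with "There may be less comfort than when the drop was first placed on the eye" and goes on to burning, stinging, itching and a foreign-body feeling. Subject-reported ocular symptoms and adverse events are both listed among the exploratory endpoints in 2.2 and are to be summarised descriptively under 14.7.

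**The concern.** A single question within the first few minutes records how a drop feels on instillation. It cannot show a later change, yet the first risk named in 1.4 is comfort falling after the drop goes in. For a sensation with no visible sign, the schedule leaves later detection to the subject's initiative. Spontaneous reports generally yield fewer and less even records than a standard question put to everyone.

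The crossover adds an attribution problem. Period 1 has a symptom baseline (1.8) and period 2 has none. If a drop 1 symptom is still present when step 1.23 is asked, nothing in the scheduled data shows that it preceded drop 2. Randomising the sequence does not cancel this. If one product causes more persisting symptoms, then in the sequence where it comes first those symptoms are added to the other product's count, which narrows the apparent difference between the drops. At stake is the by-drop reading of a listed endpoint and the completeness of the safety description in a study whose whole output is descriptive.

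**Working it through.** **1. Where symptoms and adverse events are asked about (7.1, 7.2, 7.3, Final Evaluation, Appendix D)**

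| Point in the study | Symptom question | Adverse event enquiry | Other scheduled measure |
|---|---|---|---|
| Before drop 1 (1.7–1.14) | Yes (1.8) | No | Snellen, slit lamp, logMAR |
| Between drop 1 and the 3-minute reading | Yes (1.17) | No | None |
| 3 and 10 minutes after drop 1 (1.19, 1.20) | No | No | logMAR |
| End of washout, before drop 2 (1.21–1.22) | No | No | None |
| Between drop 2 and the 3-minute reading | Yes (1.23) | No | None |
| 3 and 10 minutes after drop 2 (1.25, 1.26) | No | No | logMAR |
| Exit (F.1–F.3) | No | No | Slit lamp, Snellen |
| Unscheduled visit (7.3) | Chief complaint (U.1) | Yes (U.2) | Snellen, slit lamp |

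Appendix D also has symptom and adverse event items for remote contacts (section 5.0) and calls for an interview to collect safety data at each contact (section 6.0). No step in 7.1 or 7.2 implements that interview.

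**2. Length of the unasked interval**

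No clock time is given for 1.17 or 1.23. Step order puts each question after the left-eye drop (about 1 minute after the right-eye drop) and before 3 minutes. Taking 3 minutes as the latest time:

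- Washout counted from the right-eye drop: 90 − 3 = at least 87 minutes with no symptom question before drop 2.
- Washout counted from the 10-minute reading: 10 + 90 − 3 = at least 97 minutes.
- After drop 2: 10 − 3 = 7 minutes up to the 10-minute reading, and then none through exit.

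The protocol does not say which start of the washout applies, so both are shown.

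**3. How many subjects could be affected**

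The documents give no rate for late symptoms, so *p* below is an assumption. With the target of 25 completers, the expected number with a late symptom is 25*p*, and the chance of at least one is 1 − (1 − *p*)^25.

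| Assumed *p* | Expected subjects | Chance of at least one |
|---|---|---|
| 2% | 25 × 0.02 = 0.5 | 1 − 0.98^25 = 0.40 |
| 5% | 25 × 0.05 = 1.25 | 1 − 0.95^25 = 0.72 |
| 10% | 25 × 0.10 = 2.5 | 1 − 0.90^25 = 0.93 |
| 20% | 25 × 0.20 = 5 | 1 − 0.80^25 = 0.996 |

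These are subjects who might have a late symptom, not subjects whose symptom would be lost. Some would volunteer it.

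The plan has no figure of its own to reproduce here. Section 14.2 states that the sample size does not rest on a power analysis.

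**The case against.** One immediate tolerability question per drop is a coherent choice for a single-visit, descriptive feasibility study with no hypothesis tests. Symptoms and adverse events are exploratory, comfort is not itself an endpoint, and 1.4 lists general risks of eye drops and contact lenses rather than outcomes this study set out to measure. More questions may bring more trivial reports. All of this stands, and it limits the priority.

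Three stronger readings are tempting, and the documents support none of them.

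- A reader might infer that later reactions are captured nowhere. They are captured in part. Vision is measured by drop at 3 and 10 minutes and again by Snellen at exit, and the exit slit lamp can show redness, staining or oedema, although one examination after both drops cannot separate them. Blur and halos are in any case tied in 1.4 to continuous or prolonged use. The gap concerns reactions that are only felt.
- A reader might infer that 13.3 shuts out symptoms, because its list of documentation items includes "Adverse event (diagnosis not symptom". That item governs how an event is named. The same section requires all adverse events during enrolment to be documented, local reactions included, and 13.2.2 accepts severity as reported by the subject.
- A reader might treat the ratio of asked to unasked minutes as the share of symptoms missed. It is only elapsed time inferred from step order, and most of it is washout in which no assessment of the drop is planned.

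The symptom questionnaire procedure in Appendix C is redacted, so its recall wording and any instruction to repeat it cannot be checked.

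**Conclusion.** The point holds as a minor one. The written steps schedule one symptom question per drop, placed before the 3-minute reading, with none at the 10-minute reading, before drop 2 or at exit. Late symptom-only reactions therefore rest on spontaneous report or on the general interview in Appendix D, and a drop 1 symptom persisting to step 1.23 would be counted under drop 2.

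The interval without a question before drop 2 is at least 87 or 97 minutes. The effect on the results cannot be sized from the documents. At assumed late-symptom rates of 2% to 20%, between 0.5 and 5 of 25 completers would have such a symptom. The conclusion assumes that the questions are put in the listed step order and that the redacted procedure does not add a later one. The primary logMAR summary is unaffected.

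**What to change.** - Repeat the same open-ended question after the 10-minute readings (after 1.20 and after 1.26, before lens removal at 1.27).
- Ask it once more at the end of the washout, immediately before 1.22, and record the answer as the period 2 baseline.
- Add an adverse event enquiry line to the Final Evaluation.
- Carry these into the Time and Events table, and state in 14.7 that symptoms are summarised by drop and time point, with symptoms already present at the period 2 baseline shown separately.

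This comes to three questions and one enquiry. At an assumed minute each, that is 4 × 1 = 4 minutes in a visit estimated at 3 hours. The existing symptom form can be used. The questions come after the acuity readings, so the timing windows in section 10 are untouched, and the washout has a minimum but no stated maximum, so the extra minute fits. The downside is possibly more trivial symptom reports, for both drops alike.
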